6.2.1.6 Adverse Events Associated with Commercial Drug

Most common adverse reactions ($\geq 30\%$) included fatigue and asthenia, neutropenia, anemia, constipation, nausea, diarrhea, dyspnea, upper- respiratory tract infections, back pain, and pyrexia.

6.2.2 Contraindications

Concomitant therapy with strong CYP1A2 inhibitors should be avoided if possible. If concomitant use of a strong CYP1A2 inhibitor is unavoidable, the pomalidomide dose should be reduced to 1 mg until the strong CYP1A2 inhibitor is discontinued.

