1.0 BACKGROUND AND RATIONALE

1.1 Study Synopsis

Among patients with relapsed/refractory multiple myeloma (RRMM), selection of appropriate therapy is often challenging for the subset of patients who are especially toxicity-vulnerable on account of advanced age, comorbid medical conditions, or other factors. Traditional clinical trials typically use conservative eligibility criteria that exclude such patients in favor of young, fit patients with few comorbidities. This limits the generalizability of available trial data to more toxicity-vulnerable patients. This phase II trial of isatuximab, pomalidomide, and dexamethasone (Isa-Pom-Dex) seeks to address these challenges by selectively enrolling 49 much older and/or otherwise highly toxicity-vulnerable patients.

The starting doses of pomalidomide and dexamethasone will be 3 mg and 20 mg, respectively. Isatuximab will be administered at the standard dose of 10 mg/kg. Subjects will be treated with all three medications until progression, unacceptable toxicity, or subject withdrawal from the study.

The primary objective of this phase II study is to estimate the overall response rate (ORR) of subjects treated with the proposed regimen. Secondary objectives will include estimation of the median progression-free survival (PFS), median overall survival (OS), treatment failure-free survival (TFFS), depth of response (including achievement of bone marrow minimal residual disease [MRD]-negativity), clinical benefit rate, time to response, duration of response, and the toxicity and tolerability of therapy. All subjects on the trial will also be evaluated by Cancer and Aging Research Group-Geriatric Assessments (CARG-GA) and patient-reported outcome (PRO) measures of quality of life (QOL). Correlative blood samples (mandatory at UNC site, opt-in for other sites) will be collected with the aim of studying biomarkers of aging and frailty with a focus on both the relation to isatuximab specifically, as well as treatment response and risk for intolerability.

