5.4.2 Pomalidomide Dose Modifications/Delays

Allowable dose adjustments/reductions are outlined in Table 3. If 1 mg is not tolerated despite maximal supportive care, then pomalidomide should be permanently discontinued and other study drugs may be continued if felt to be appropriate by the treating clinician.

Table 3 Pomalidomide Dose Levels/Modifications

Dose Level	Dose (mg)
+1*	4 mg
0	3 mg
-1	2 mg
-2	1 mg
-3	Discontinue

**If after 3-cycles, the patient has SD (<MR) and has not experienced any grade ≥ 3 hematologic toxicities or treatment-related grade ≥ 2 non-hematologic toxicities, at the investigator's discretion, the dose of pomalidomide may be increased to 4 mg beginning*

with cycle 4. Pomalidomide dose increases to 4 mg may also be considered in other situations on a case-by-case basis after discussion with the PI.

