5.4.2.1 Mid-cycle pomalidomide dose reductions

Per modification rules in **Table 4** and **Table 5**, subjects may warrant pomalidomide dose reduction mid-cycle. Insurance and/or pharmacy delivery limitations may prevent receipt of a new bottle of pomalidomide at the reduced dose until the next cycle, and pomalidomide capsules cannot be cut in half. If this occurs, the treating clinician may do one of the following:

- A) Have the subject take one pill **EVERY OTHER DAY** of their current dose of pomalidomide, to complete the usual three weeks of pomalidomide for the current cycle and then switch to the new daily dose for next cycle
OR
- B) Remain off pomalidomide until the subject receives a new supply at the lower dose and is due to start the next cycle.

Decisions should be made at the discretion of the treating clinician based on the urgency of continuing pomalidomide and other relevant considerations such as subject's ability to comply with every other day dosing strategy.

As an example, a hypothetical subject is on 3 mg pomalidomide and on day 10 of the current cycle of Isa-Pom-Dex, the subject experiences a toxicity requiring pomalidomide dose reduction to 2 mg. The treating clinician has the following options: A) instruct the subject to take pomalidomide 3 mg every **OTHER** day until day 21 of the current cycle, followed by the standard 7-day break; or B) instruct the subject to remain off pomalidomide for the remainder of the current cycle. In either case, the subject would begin a pomalidomide dose of 2 mg on day 1 of the next cycle.

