13.0 APPENDICES

13.1 Appendix A. Prohibited Medications or Those to be Used with Caution

Isatuximab

No drug-drug interaction has been observed between isatuximab and other drugs used in combination.

Pomalidomide

The following information is from Section 7 (Drug Interactions) of the package insert. Additional information may be found here:

https://www.accessdata.fda.gov/drugsatfda_docs/label/2017/204026s019lbl.pdf

Co-administration of pomalidomide with the following drugs did not increase pomalidomide exposure to a clinically significant extent: ketoconazole (a strong CYP3A4 and P-gp inhibitor), carbamazepine (a strong CYP3A4 inducer) and dexamethasone (a weak to moderate inducer of CYP3A4). Co-administration of pomalidomide with drugs that are CYP1A2 inducers has not been studied.

CYP1A2 Inhibitors: Co-administration of fluvoxamine (a strong CYP1A2 inhibitor) with pomalidomide increased mean [90% confidence interval] pomalidomide exposure by 125% [98% to 157%] compared to pomalidomide alone in healthy subjects. Co-administration of fluvoxamine in the presence of ketoconazole (a strong CYP3A4 and P-gp inhibitor) with pomalidomide increased mean pomalidomide exposure by 146% [126% to 167%] compared to pomalidomide administered alone in healthy subjects, indicating the predominant effect of CYP1A2 inhibition in the increase of pomalidomide exposure [*see Dosage and Administration (2.2) and Drug Interactions (7.1)*].

Strong CYP3A4 and P-gp Inhibitors: Co-administration of ketoconazole (a strong CYP3A4 and P-gp inhibitor) in 16 healthy male subjects increased AUC of pomalidomide by 19% compared to pomalidomide administered alone.

Drugs that Induce Pomalidomide Metabolism

Strong CYP1A2 Inducers: Co-administration of pomalidomide with drugs that are CYP1A2 inducers has not been studied and may reduce pomalidomide exposure.

Strong CYP3A4 Inducers: Co-administration of carbamazepine to 16 healthy male subjects decreased AUC of pomalidomide by 20% with a 90% confidence interval [13% to 27%] compared to when pomalidomide was administered alone.

Dexamethasone: Co-administration of multiple doses of 4 mg pomalidomide with 20 mg to 40 mg dexamethasone (a weak to moderate inducer of CYP3A4) to patients with multiple myeloma had no effect on the pharmacokinetics of pomalidomide compared to when pomalidomide was administered alone.

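### The fixed 1 mg pomalidomide rule for an unavoidable strong CYP1A2 inhibitor gives no reduction to a subject already at 1 mg, whose exposure then roughly doubles or more on the protocol's own figures

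*Combined protocol and SAP*

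**What the plan says.** Section 6.2.2 (pomalidomide contraindications) first tells sites to keep subjects off strong CYP1A2 inhibitors where they can. If use is unavoidable, "the pomalidomide dose should be reduced to 1 mg until the strong CYP1A2 inhibitor is discontinued". The sentence gives one absolute target and does not refer to the subject's current dose level.

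Table 3 in section 5.4.2 sets four dosing levels and then discontinuation:

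- Level 0 is the starting dose: "The starting doses of pomalidomide and dexamethasone will be 3 mg and 20 mg, respectively" (section 1.1).
- Level +1 is an optional escalation, under which "the dose of pomalidomide may be increased to 4 mg".
- Level -1 is 2 mg. Section 5.4.2.1 illustrates how it is reached: "the subject experiences a toxicity requiring pomalidomide dose reduction to 2 mg".
- Level -2 is 1 mg. Nothing lies below it but stopping: "If 1 mg is not tolerated despite maximal supportive care, then pomalidomide should be permanently discontinued".

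Appendix A gives the size of the interaction. Fluvoxamine, described there as a strong CYP1A2 inhibitor, "with pomalidomide increased mean [90% confidence interval] pomalidomide exposure by 125% [98% to 157%] compared to pomalidomide alone in healthy subjects". With ketoconazole also present, the stated increase is 146% (126% to 167%).

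**The concern.** Level -2 is a dosing level in its own right, reached under the toxicity rules of Tables 4 and 5. A subject there who needs a strong CYP1A2 inhibitor is already at the dose that section 6.2.2 prescribes. A site that follows the sentence exactly makes no change, while Appendix A says exposure will rise substantially. The rule acts as a reduction at the upper levels and does nothing at the lowest one.

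What is at stake is first the safety of a subject whose dose was lowered because a higher one was not tolerated. There is also a knock-on within section 5.4.2. Intolerance at 1 mg leads to permanent discontinuation of pomalidomide, and here that judgement could be made at about twice the exposure that 1 mg normally gives.

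**Working it through.** **Inputs.**

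- Rule: 1 mg with an unavoidable strong inhibitor (section 6.2.2).
- Levels: 4, 3, 2 and 1 mg (Table 3).
- Increase with fluvoxamine: 125%, 90% CI 98% to 157% (Appendix A).
- Increase with fluvoxamine in the presence of ketoconazole: 146%, interval 126% to 167% (Appendix A, where this interval carries no label of its own).

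**Step 1: read the stated figure.** Appendix A says that exposure increased by 125%, so the multiplier is 1 + 1.25 = 2.25, with limits 1.98 and 2.57. With ketoconazole it is 2.46, with limits 2.26 and 2.67. As a check, the geometric midpoints of the intervals are √(1.98 × 2.57) = 2.256, an increase of 125.6% against 125% stated, and √(2.26 × 2.67) = 2.456, an increase of 145.6% against 146% stated. The figures are coherent on this reading. The midpoint check alone would not rule out a 1.25-fold reading (√(0.98 × 1.57) = 1.24), but the wording does, because it gives the amount of the increase.

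**Step 2: subject already at 1 mg.** The dose change under the rule is 1 mg - 1 mg = 0. Exposure with the inhibitor divided by exposure without it, at the same dose, is 2.25 (1.98 to 2.57), or 2.46 (2.26 to 2.67) with ketoconazole. The dose is the same on both sides, so no dose-proportionality assumption is needed.

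**Step 3: subjects at other levels.** Here two different doses are compared, so exposure must be assumed proportional to dose between 1 mg and 4 mg. The documents do not state this. The ratio is (1 mg × multiplier) / assigned dose.

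| Assigned dose | Strong inhibitor | Change on the mean | With ketoconazole |
|---|---|---|---|
| 4 mg (+1) | 2.25/4 = 0.56 (0.50 to 0.64) | -44% | 0.62 (0.57 to 0.67) |
| 3 mg (0) | 2.25/3 = 0.75 (0.66 to 0.86) | -25% | 0.82 (0.75 to 0.89) |
| 2 mg (-1) | 2.25/2 = 1.125 (0.99 to 1.285) | +12.5% | 1.23 (1.13 to 1.34) |
| 1 mg (-2) | 2.25/1 = 2.25 (1.98 to 2.57) | +125% | 2.46 (2.26 to 2.67) |

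At 3 mg and 4 mg the whole interval lies below 1, so the rule lowers exposure. At 2 mg with fluvoxamine alone, the interval runs from 1% below to about 29% above the assigned dose and so reaches parity. At 1 mg the whole interval is about a doubling or more.

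**The case against.** The strongest reply is that this is one unaddressed case and not a contradiction. Section 6.2.2 contains no calculation and promises no exposure target. One milligram is the lowest level in Table 3 and the lowest capsule strength listed in section 6.2.1.2, so the instruction is compatible in form with both.

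There are also safeguards. Inhibitors are to be avoided in the first place. Exclusion 4.2.18 bars subjects on medications listed in section 5.7 or Appendix A that cannot be stopped or replaced. The holding and stopping rules in section 5.4.2 and Tables 4 and 5 continue to apply. Section 6.2.2 also limits the reduction to the period of inhibitor use. The interaction data come from healthy subjects.

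Much of this stands. The documents give no frequency for strong CYP1A2 inhibitor use or for reaching 1 mg. Section 1.7.1 reports pomalidomide reductions in 43% of the isatuximab arm of ICARIA-MM, but not how far down they went. The case should be uncommon.

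The gap itself remains. Exclusion 4.2.18 is applied at baseline and does not cover an inhibitor started during treatment. Appendix A mixes prohibited drugs with drugs to be used with caution, so it is unclear whom the exclusion catches. Section 5.7 does not name CYP1A2 inhibitors. The toxicity rules act only after an event has occurred. Section 6.2.2 itself provides for unavoidable use, and that provision is empty at level -2.

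**Conclusion.** The point holds for subjects at 1 mg. Followed exactly, the rule gives them no reduction, while exposure rises by 125% (98% to 157%) on Appendix A's figures, or by 146% with ketoconazole. This rests only on the healthy-subject interaction data carrying over to trial subjects.

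At 2 mg the finding is weaker. Under assumed dose proportionality, the rule leaves exposure about level with or slightly above that of 2 mg alone.

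Three stronger readings might be inferred, and the documents do not support them:

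- **That subjects at 2 mg are clearly over-exposed.** The interval for the strong inhibitor alone includes no increase, and the comparison needs an assumption that the protocol does not make.
- **That subjects at 2 mg are returned to the exposure of the dose they left.** They left 3 mg. Under the same assumption the rule gives 2.25 mg-equivalents, and even the upper limit with ketoconazole, 2.67, is below 3.
- **That the Table 10 boundary or treatment failure-free survival is distorted.** No such effect is shown. Table 10 counts only attributed non-hematological events of Grade 4 or higher, and section 1.7.1 says that dose reductions in ICARIA-MM were mainly for neutropenia and infections. The point concerns subject safety and a clear instruction to sites, not the trial's statistical design.

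**What to change.** Reconcile section 6.2.2 with Table 3 and Appendix A by amendment. The inhibitor rule should state what applies to a subject already at a reduced dose level when a strong CYP1A2 inhibitor becomes unavoidable, and in particular to a subject already at 1 mg. The sponsor's clinical team must decide the content. No dose or clinical rule is proposed here. The cost is a change of wording, with no additional patients, visits or procedures and no change to the sample size or the analysis.

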6.2.3 Commercial Drug Description and Management: Dexamethasone

6.2.3.1 Brief Description

Dexamethasone is a practically white or white, odorless, crystalline powder that is a synthetic glucocorticoid. Glucocorticoids produce varied metabolic effects.

6.2.3.2 Supplier/How Supplied

Dexamethasone is commercially available and therefore is to be purchased by a third party. Dexamethasone is available in seven potencies (0.5 mg, 0.75 mg, 1mg, 1.5 mg, 2 mg, 4 mg, and 6 mg) in tablet form.

6.2.3.3 Dosage and Administration

See

Treatment Dosage and Administration

Note: Dexamethasone is to be given with a snack/light meal to reduce gastric irritation.

Refer to package insert for complete dispensing instructions available at:
[http://docs.boehringer-
ingelheim.com/Prescribing%20Information/PIs/Roxane/Dexamethasone/Dexamethasone%20Tablets%20Solution%20and%20Intensol.pdf](http://docs.boehringer-
ingelheim.com/Prescribing%20Information/PIs/Roxane/Dexamethasone/Dexamethasone%20Tablets%20Solution%20and%20Intensol.pdf)

6.2.3.4 Storage and Stability

Store dexamethasone at 20°C-25°C (68°F-77°F).

6.2.3.5 Handling and Disposal

Local requirements for disposal of hazardous drugs should be followed at each participating clinical site.

Please see UNC policy on hazardous drugs:
<https://unchealthcare-uncmc.policystat.com/policy/4734545/latest/>

6.2.3.6 Adverse Events Associated with Dexamethasone

Gastrointestinal: Nausea, vomiting, anorexia, increased appetite, weight gain; aggravation of peptic ulcers.

Dermatologic: Rash, skin atrophy, facial hair growth, acne, facial erythema, ecchymoses. Genitourinary: Menstrual changes (amenorrhea, menstrual irregularities).

Neurologic: Insomnia, euphoria, headache, vertigo, psychosis, depression, seizures, muscle weakness.

Cardiovascular: Fluid retention and edema, hypertension; rarely, thrombophlebitis. Ocular: Cataracts, increased intraocular pressure, exophthalmos.

Metabolic: Hyperglycemia, decreased glucose tolerance, aggravation or precipitation of diabetes mellitus, adrenal suppression (with Cushingoid features), hypokalemia.

Hematologic: Leukocytosis.

Other: Osteoporosis (and resulting back pain), appearance of serious infections including herpes zoster, varicella zoster, fungal infections, Pneumocystis carinii, tuberculosis; muscle wasting; delayed wound healing; suppression of reactions to skin tests.

6.2.3.7 Contraindications

Contraindicated in systemic fungal infections.

Use in Pregnancy

Pregnancy Category C: Corticosteroids have been shown to be teratogenic in many species when given in doses equivalent to the human dose.

Use in Nursing Women

Systemically administered corticosteroids appear in human milk and could suppress growth, interfere with endogenous corticosteroid production, or cause other adverse effects on the nursing infant.

Overdose

Treatment of overdosage is by supportive and symptomatic therapy. In the case of acute overdosage, according to the subject's condition, supportive therapy may include gastric lavage or emesis.

7.0 CLINICAL ASSESSMENTS

Clinical assessments will be performed as outlined in the **Time and Events Table** in EVALUATIONS AND ASSESSMENTS

7.1 Evaluations and Assessment

7.1.1 Concomitant Medications

All concomitant medication and concurrent therapies will be documented at screening, within 7 days prior to Day 1 of the study treatment and throughout the study at each treatment visit and at the end of treatment. Dose, route, unit frequency of administration, and indication for administration and dates of medication will be captured.

7.1.2 Demographics

Demographic information (date of birth, gender, race) will be recorded at Screening.

7.1.3 Medical History

Relevant medical history, including history of current disease, other pertinent history, and information regarding underlying diseases will be recorded at time of screening, within 21 days prior to Day 1 of the study treatment and a focused medical history on symptoms/toxicity will be performed thereafter throughout the study.

7.1.4 Physical Examination/Vital Signs/Performance Status

A complete physical examination including height (at screening only), weight, Karnofsky Performance status (Appendix B. Karnofsky Performance Status Scale) and vital signs (i.e., temperature and blood pressure).

Qualified staff (MD, DO, NP, or PA) will complete the exams.

New abnormal physical exam findings must be documented and will be followed by a physician or other qualified staff at the next scheduled visit.

7.1.5 Adverse Events

Any patient who receives treatment on this protocol will be evaluable for toxicity. Events should be assessed per NCI-CTCAE criteria v5.0. Information regarding occurrence of adverse events will be captured throughout the study, including as outlined in the time and events table (see section 8.1). Duration (start and stop dates), severity/grade, outcome, treatment and relation to study drug will be recorded in the case report form (CRF).

7.2 MM Disease Assessment

7.2.1 Beta-2-Microglobulin and Lactate Dehydrogenase (LDH)

Only required at D1 of cycle 1, prior to starting maintenance, and at the end of study treatment.

7.2.2 Monoclonal protein (M-protein) assessments

- 1) Serum protein electrophoresis (SPEP) with immunofixation electrophoresis (IFE),
- 2) Serum free light chain assay,
- 3) Serum immunoglobulin (Ig) quantification
- 4) 24-hour urine protein electrophoresis (UPEP) with IFE

7.2.3 Bone marrow (BM) Aspirate and Biopsy

BM aspirate and biopsy for morphology, flow cytometry, cytogenetics, and fluorescence *in situ* hybridization (FISH), and correlative research, will be collected per the Time and Events Table at screening and at EOT timepoints. BM aspirate and biopsy for morphology and flow cytometry (plus cytogenetics and FISH if clinically warranted) will also be collected as needed to assess response status, such as CR or PD. Commercially available minimal residual disease (MRD) assessments by next-generation sequencing with a minimum sensitivity of 1×10^{-5} should be performed if possible on bone marrow, in subjects who are in serological CR. Results will be reported on the eCRF with other bone marrow results.

7.3 Clinical Laboratory Assessments

Timing of clinical assessments should follow the schedule presented in the Time and Events Table.

All clinical laboratory testing should be performed locally. There are no central laboratory tests with the sole exception of correlative studies.

7.3.1 Hematology

Complete blood count should be accompanied by a white blood cell differential.

7.3.2 Serum Chemistry Profile

Serum chemistries must include sodium, potassium, chloride, CO₂, BUN, creatinine, glucose, and calcium. Albumin, total protein, total bilirubin, AST, ALT, alkaline phosphatase should be included on specific dates as outlined in the Time and Events Table.

7.3.3 Pregnancy Test

Frequent pregnancy testing is required for females of childbearing potential who receive pomalidomide. See the **Time and Events Table**.

Because of the embryo-fetal risk, POMALYST is available only through a restricted program under a Risk Evaluation and Mitigation Strategy (REMS) called “**POMALYST REMS.**”

Required components of the **POMALYST REMS** program include the following:

- Prescribers must be certified with the **POMALYST REMS** program by enrolling and complying with the REMS requirements.
- Patients must sign a Patient-Physician Agreement Form and comply with the REMS requirements. In particular, female patients of reproductive potential who are not pregnant must comply with the pregnancy testing and contraception requirements and males must comply with contraception requirements.
- Pharmacies must be certified with the **POMALYST REMS** program, must only dispense to patients who are authorized to receive POMALYST, and comply with REMS requirements.

Further information about the **POMALYST REMS** program is available at www.CelgeneRiskManagement.com or by telephone at [name].

If a woman becomes pregnant while taking isatuximab, treatment with isatuximab should be discontinued and the pregnancy should be followed until its outcome.

7.3.4 Type and Screen, Red Blood Cell Phenotyping

Should be obtained prior to starting isatuximab.

7.4 Clinical Imaging

7.4.1 CT / MRI / PET-CT

Computerized Tomography (CT), magnetic resonance imaging (MRI) or PET-CT should be performed with screening if a subject is known to have an extramedullary plasmacytoma. If done, the same technique should be employed as clinically indicated during the study treatment (including if relevant to confirm response), and again at the end of study treatment.

